4.7.3 Prohibited Concomitant Medications

The following treatments and/or medications are prohibited while on study:

- Any other investigational product taken within 4 weeks prior to Day 1 of Cycle 1 and/or through the entire study treatment period is not allowed. For this purpose "Other investigational product" has to be intended as any agents tested in clinical trials, even those which are tested for indications that are already approved.

- Anticancer agents. If such agents are required, then the patient must discontinue study treatment prior to receiving the anti-cancer therapy and disease progression should be documented. For patients at Cycles 1 through 6, it is recommended to contact the Medical Monitor prior to study treatment discontinuation. Every effort should be made to complete the End of Study Treatment visit **prior** to the patient starting any AML treatment regimen other than pracinostat/placebo + AZA.
- Hydroxyurea is allowed until Cycle 1, Days 1-14, to reduce WBC count to <30,000 μ L prior to Day 1. After Cycle 1, Day 14, hydroxyurea is prohibited.
- HDAC inhibitors.
- Medications with a known risk of prolonging the QT interval and/or causing Torsades de Pointes. ([Appendix I](#)).
- Herbal products are not allowed throughout the study. Subjects should stop using these prior to the first dose of study treatment.

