6 DATA HANDLING METHODS

6.1 MISSING DATA

6.1.1 Date Values

In cases of incomplete dates, the missing component(s) will be assumed as the most conservative value(s) possible.

Actual data values as they appear in the original CRFs will be shown in the data listings.

For the following dates specific imputation rules are defined:

Imputation of time to event variable dates:

Missing dates for time to event variables have to be avoided as far as possible.

The difference between the start date and the event date is calculated as time to event for the main efficacy variable and for some of the secondary variables.

Therefore the imputation of partial or complete missing event dates has to be handled using the most conservative approach. It is especially necessary to distinguish between active treatment and placebo group in this respect. As events analysed in this study are “negative” events, the following rules can be considered as conservative.

Imputation rules for missing event date

for patients who received active treatment (Pracinostat):

- If “day” is the only missing field, impute the “day” as the first day of the month documented or the last visit date within the documented month, where the absence of the event is documented.
- If “day” and “month” are missing, impute the “day” and “month” as 01 January of the year documented or the last visit date within the documented year, where the absence of the event is documented.
- If “day”, “month”, and “year” are all missing, the date of event is imputed as the date of the last visit date where the absence of the event is documented.

for patients who received Placebo:

- If “day” is the only missing field, impute the “day” as the last day of the month documented or the last visit date within the documented month, where the absence of the event is documented.
- If “day” and “month” are missing, impute the “day” and “month” as 31 December of the year documented or the last date within the documented year where the absence of the event is documented.
- If “day”, “month”, and “year” are all missing, the date of event is imputed as the date of the last visit documented where the absence of the event is documented.

For missing start dates of duration of response, rules for placebo should be used for pracinostat and viceversa, to be conservative.

Imputation of time of new AML therapies:

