Missing dates for new AML therapies (either those started after study treatment stop or concomitant to study treatment stop) have to be avoided as far as possible.

The imputation of partial or complete missing start and end dates of new AML therapies have to be handled using the most conservative approach. It is especially necessary to distinguish between active treatment and placebo group in this respect. As events analysed in this study are “negative” events, the following rules can be considered as conservative.

General rules for imputation are:

- any imputed date should be before the date of death or the last day the patient was alive
- the end date of the therapy should be greater or equal to the start date of the therapy

If more than one new AML therapy is given to a patient during study period only the first start date of the new therapies is relevant for the censoring processes (selection of the first start date will be done after any imputations).

Imputation rules for missing **start date** of the first new AML therapy

for patients who received **active treatment** (Pracinostat):

- If “day” is the only missing field, impute the “day” as the first day of the month documented. If month and year are equal to the start of the study treatment impute the date as the first treatment day.
- If “day” and “month” are missing, impute the “day” and “month” as 01 January of the year documented or the start of the study treatment if the year is the same as for treatment start.
- If “day”, “month”, and “year” are all missing, the date of the start of the new AML therapy is imputed as the date of the start of the study treatment.

for patients who received **Placebo**:

- If “day” is the only missing field, impute the “day” as the last day of the month documented.
- If “day” and “month” are missing, impute the “day” and “month” as 31 December of the year documented or as 01 January if the year is the same as for treatment start.
- If “day”, “month”, and “year” are all missing, the date of event is imputed as 01 January of the year when the study treatment started.

Imputation rules for missing **end date** of the first new AML therapy

for patients who received **active treatment** (Pracinostat):

-
- If “day” is the only missing field, impute the “day” as the last day of the month documented.
 - If “day” and “month” are missing, impute the “day” and “month” as 31 December of the year documented.

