PFS is defined as the time from the date of randomization until the date of relapse (progression) or death from any cause, whichever occurs first.

The analysis set will be the ITT set.

Censoring rules are:

- Time to relapse (progression) will be censored at the date of the last assessment of patient status that excluded relapse (progression). Current disease status field in the CRF page of long-term follow-up visits is to be considered as adequate information.
- In case of no disease assessments, censoring will be at the date of randomization.

PFS will be analyzed using the same methods as those used for OS (Kaplan Meier estimates and stratified log-rank test).

In addition, the influence of additional censoring criteria on PFS in the two treatment groups will be analyzed, namely censoring at the start date of a new cancer therapy instead of censoring at the date of the last assessment in the study.

Duration of Morphologic Complete Remission (CR)

Duration of CR is defined as the time from the date of achievement of CR until the date of relapse (progression). Kaplan-Meier methods will be used to estimate duration of response in each treatment group. Duration of CR will be analyzed using the same methods as those used for OS (Kaplan Meier estimates and stratified log-rank test).

Censoring rules will include the following:

- Time will be censored at the date of the last adequate assessment of patient status that excluded relapse (progression). In case of no disease assessments after CR, censoring will be at the date of CR.
- Time will be censored at the start of interceding therapies

The analysis set will be the ITT set limited to patients who achieve a CR in absence of interceding therapies.

Duration of Composite Complete Remission (cCR)

Duration of cCR response is defined as the time from the date of achievement of either CR, CRi or MLFS until the date of relapse (progression) and will be analyzed as the duration of CR response.

Censoring rules will include the following:

- Time will be censored at the date of the last assessment of patient status excluding relapse. In case of no disease assessments after cCR, censoring will be at the date of cCR.
- Time will be censored at the start of interceding therapies

The analysis set will be the ITT set limited to patients who achieve a cCR in absence of interceding therapies.

Time to Morphologic Complete Remission (CR)

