Explorative	PFS	ITT	ECOG, RISK (randomization)	Log-rank	Censor at time of new therapy	sensitivity
Explorative	Duration of CR	ITT	ECOG, RISK (randomization)	Log-rank	Censor at time of new therapy	Primary analysis for this endpoint
Explorative	Duration of cCR	ITT	ECOG, RISK (randomization)	Log-rank	Censor at time of new therapy	Primary analysis for this endpoint
Explorative	Time to CR	ITT	ECOG, RISK (randomization)	Long-rank	none	Primary analysis for this endpoint
Explorative	CR within 6 cycles	ITT	ECOG, RISK (randomization)	CMH	none	Primary analysis for this endpoint
Subgroups	OS, CR, CRc CR _{MRD} - Transfusion independence	ITT as relevant (only the primary set)	ECOG, RISK (randomization) if feasible Otherwise unstratified	Log-rank or CMH or Logistic regression (as relevant)	Features used in the main analysis of each endpoint	Not Applicable

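### Incomplete start dates of new AML therapy are imputed early for pracinostat and mostly late for placebo, but they act as censoring times; in duration of CR and cCR this can favour pracinostat, opposite to the SAP's conservative label

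*SAP*

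**What the plan says.** SAP 6.1.1 has separate rules by arm for incomplete start dates of a new AML therapy. It calls them conservative on the ground that the events analysed are unfavourable.

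- **Day missing.** Pracinostat is completed "as the first day of the month documented. If month and year are equal to the start of the study treatment", and in that last case the first treatment day is used. Placebo is completed "as the last day of the month documented".
- **Day and month missing.** Pracinostat goes to 1 January, or to treatment start if the year is the same. Placebo goes to "31 December of the year documented or as 01 January if the year is the same as for treatment start".
- **Date wholly missing.** Pracinostat goes to treatment start, placebo to 1 January of the treatment-start year.
- **Limits.** Imputed dates are bounded by death or last known alive. No limit refers to a documented relapse.

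The role of the date is explicit in the same section: "only the first start date of the new therapies is relevant for the censoring processes". SAP 7.8 confirms it as the censoring point. For duration of CR and of cCR, SAP 8.3 states "Time will be censored at the start of interceding therapies". The SAP 13 rows for these two endpoints carry the feature "Censor at time of new therapy" and are labelled the primary analysis for the endpoint.

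Two further passages bear on direction. SAP 6.1.1 reverses the arms for another kind of date: "For missing start dates of duration of response, rules for placebo should be used for pracinostat and viceversa, to be conservative". Protocol 4.7.3 says that if another anticancer agent is needed, "the patient must discontinue study treatment prior to receiving the anti-cancer therapy and disease progression should be documented".

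**The concern.** The reason given for the therapy-date rules is the one given for event dates. It does not carry over. Moving a relapse earlier hurts the arm it belongs to. Moving a censoring time earlier can remove that arm's relapse from the analysis.

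The protocol expects progression to be documented when a patient goes on to other anticancer treatment, so a relapse shortly before the therapy start is a natural sequence. An early imputed date then jumps over the relapse and a late one does not. Two patients with identical records would be analysed differently because of their arm, and the label would tell the reader that the distortion runs the other way. The swap for response start dates shows that the SAP recognises that direction depends on use, but it makes no such swap here.

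**Working it through.** The plan gives no figure for this point, so there is none to reproduce.

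**1. One record in both arms.** Treatment starts in 2018, relapse is on 10 June 2019, new therapy starts on 20 June 2019, and the day is missing. Pracinostat is imputed to 1 June and censored there, so the relapse is lost. Placebo is imputed to 30 June, so the relapse counts. With only the year known, pracinostat goes to 1 January 2019 and the relapse is lost. If CR itself came later in 2019 and imputed dates define the responder set, the patient leaves the set. Placebo goes to 31 December, or the latest date allowed by death or last known alive, and the relapse counts.

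**2. How often, with the day missing.** Let therapy start on day *d* of a month and relapse come *g* days earlier. The pracinostat relapse is lost when *d* − *g* > 1. Over 2018–2021 the mean month is 1461/48 = 30.4375 days, so with start days spread evenly the share lost is 1 − (*g* + 1)/30.4375:

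- *g* = 7: 1 − 8/30.4375 = 0.737
- *g* = 14: 1 − 15/30.4375 = 0.507
- *g* = 21: 1 − 22/30.4375 = 0.277

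For placebo the relapse would have to fall after the last day of the therapy month. It cannot, so the share is 0.

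**3. Effect on duration of CR when the arms do not differ.** From the documents: CR rates 0.33 and 0.20 (SAP 5.5) and 250 patients per arm, giving about 83 and 50 responders; accrual as in Protocol 9.11; stratified log-rank at one-sided 0.025. Assumed: 40% unfavourable risk (hazard × 1.5), 35% ECOG 2 (× 1.3), CR at 56–240 days, median time to relapse about 10 months, and the shares and gaps in the table. The table gives the HR relative to the analysis with true dates, by share of therapy dates missing the day.

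| Therapy after relapse (assumed) | 2% | 5% | 10% | 20% |
|---|---|---|---|---|
| 50% of relapsers, within 1–30 days | 0.996 | 0.989 | 0.979 | 0.956 |
| 80% of relapsers, within 1–14 days | 0.989 | 0.972 | 0.945 | 0.891 |
| Unrelated to relapse | 1.000 | 1.000 | 1.000 | 1.000 |

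One-sided rejection at 5% and 10% missing is 0.029 and 0.032 in the first setting (true dates 0.027), and 0.034 and 0.044 in the second (true dates 0.028). The Monte Carlo SE is 0.002. With 5% of records year-only for both start and end, the HR is 0.986 and 0.976 in these settings, and 1.003 if unrelated.

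A simpler simulation (82 v 50 responders, median duration 10 months, 60% of relapsers treated within 1–28 days) gave HR 0.99, 0.97 and 0.94 at 5, 10 and 20% day-missing. On average 0.8, 1.5 and 3.0 of about 53 pracinostat relapses were lost, and no placebo relapse.

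**4. Other uses of the same dates.**

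- *PFS and RFS sensitivity analyses.* Read literally, SAP 8.3 replaces only the censoring date of event-free patients. On that reading the simulated PFS HR is 1.000. If progressions after therapy start are dropped, it is 0.993 and 0.986 (first setting) or 0.982 and 0.964 (second) at 5% and 10%.
- *Time to CR (SAP 8.3).* CR is a favourable event, so an early censoring date can cost pracinostat a CR. The rule works against pracinostat.
- *OS censored at new therapy (SAP 8.1.2).* Deaths follow the therapy start, so no further death is dropped. Pracinostat only loses event-free time, which is slightly against it.
- *Whether a CR, CR without MRD or CRc is free of interceding therapy (SAP 8.2).* The SAP does not say whether imputed dates decide this. If they do, early dates cost pracinostat responders: under 0.1 of 83 CRs at 5% day-missing, and about 0.2–0.4 points of the planned 13-point difference at 5% year-only.

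**5. Placebo starts set to 1 January of the treatment-start year.** Such a date can precede first dose. Under SAP 7.8, a therapy that started and ended before Cycle 1 Day 15 is ignored. Example: first dose 10 June, Day 15 on 24 June, start known to the year only, end recorded as June. Placebo becomes 1 January to 1 June and is ignored. Pracinostat becomes 10 June to 30 June and is censored at Day 15. The same happens when the placebo end date is known only to that year, because it is then set equal to the start. Both patterns should be rare.

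**The case against.** The strongest reply is that the effect is conditional and probably small. A loss needs an incomplete therapy date, a relapse, and that relapse between the imputed and the true start. Protocol 4.7.3 gives no interval between progression and therapy. At 2% of days missing the HR is 0.989–0.996, and in the milder setting at 5% the rejection rate cannot be told from its value with true dates. The larger effects need 10–20% missing or very prompt therapy, and neither comes from the documents. The SAP also asks that missing dates be avoided, lists new AML treatment and both durations by patient, and lets the blind data review add sensitivity analyses. All of this stands as a limit on size. None of it makes the rule conservative in these two analyses.

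The second reply is that the label is right elsewhere: Time to CR, OS censored at new therapy and, if imputed dates decide it, the alpha-controlled response endpoints. That also stands. A reader might infer that the rule favours pracinostat throughout, or that reversing the arms would cure it. The documents support neither, because the direction changes with the use.

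A reader might also take the loss to be one-sided in every pattern. That is exact only for relapses removed by censoring. Under the 1 January patterns some placebo responders can leave the responder set too, as pracinostat responders do: 0.4 against 1.1 patients on average at 20% incomplete dates of mixed pattern.

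**Conclusion.** The point holds for the main analyses of duration of CR and of cCR. When the therapy start lacks the day, or lacks day and month in a year after treatment start, a relapse between the imputed and the true start is lost for pracinostat and kept for placebo. This favours pracinostat, against the stated direction.

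The size rests on two quantities that are not in the documents. If therapy tends to follow relapse, the null HR is about 0.97–0.99 at 5% day-missing and 0.95–0.98 at 10%. If therapy is unrelated to relapse, it is 1.00. The PFS and RFS sensitivity analyses move only if progressions after therapy start are dropped.

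It would be wrong to infer that the trial's main conclusion or its alpha is compromised. Primary OS is not censored at new therapy (SAP 8.1), the two duration endpoints are exploratory, and on the alpha-controlled response endpoints any effect runs against pracinostat. The change should still be made, because identical records are treated differently by arm under a label that misstates the direction.

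**What to change.** For new-therapy start dates used as censoring times, replace the arm-specific rules in SAP 6.1.1 with one arm-blind rule:

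- Use the midpoint of the possible window.
- Bound it above by death or last known alive.
- Bound it below by first dose (randomization if never dosed). For duration, PFS and RFS, also bound it below by a documented relapse or progression, or the last relapse-free assessment, inside the window. The latest of these applies.

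The relapse bound matters. A plain midpoint still loses 26% of relapses at a 7-day gap and 3% at 14 days, although equally in both arms.

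Remove the conservative label. Keep arm-specific extremes only as a labelled stress test, with the direction set for each use: late pracinostat and early placebo for duration, PFS and RFS; early pracinostat and late placebo for Time to CR, OS censored at new therapy, and deciding whether a response counts. State in SAP 8.3 whether PFS and RFS events after therapy start are censored, and in SAP 8.2 whether imputed dates decide if a response counts.

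The cost is SAP wording and one date-derivation program. The downside is that the lower bound may keep a few relapses that truly followed therapy, under the same rule in both arms.

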 - If “day”, “month”, and “year” are all missing or if “ongoing” is documented, the date is imputed as the last date known alive .

for patients who received **Placebo**:

- If “day” is the only missing field, impute the “day” as the first day of the month documented.
- If “day” and “month” are missing, impute the “day” and “month” as 01 January of the year. If the year documented is equal to the year of the start of the study treatment, the date of the end of the new AML treatment is imputed as the start date of the new AML treatment.
- If “day”, “month”, and “year” are all missing or “ongoing” is documented, the date is imputed as the last date known alive.

Imputation of Adverse Event dates:

Missing AE dates will be queried as far as possible taking other information (eg, relatedness to study drug, first intake of study drug) into account.

For missing AE start or end date, imputation rules follow the principle that the AE is regarded as treatment-emergent AE (TEAE) when a connection to the start and end of the treatment period could not be excluded (by the documented partial dates or other relevant information in the CRF).

Imputations of adverse events are used for slotting events to the appropriate study time periods and for sorting in data listings. They will not be used to calculate duration of AEs. If an AE start or end date is missing, then the duration of the AE will be set to missing.

Remaining missing dates will be imputed as follows:

For AE start date, imputation rule is to conservatively capture AEs with missing start dates as treatment-emergent AEs (TEAEs):

- If “day” is the only missing field, impute the “day” as the first dose date if their “month” are the same. Otherwise impute the “day” as the first day of the month documented.
- If “day” and “month” are the only missing fields, impute the “day” and “month” as the first dose date if their “year” is the same. Otherwise impute the “day” and “month” as the first of January of the year documented.
- If “day”, “month”, and “year” are all missing, to be conservative, the AE will be assumed to occur on the same day as the first dose was administered.

For AE end date, imputation rule is to conservatively capture AEs with missing end dates as treatment-emergent AEs (TEAEs):

- If “day” is the only missing field, impute the “day” as the last day of the month documented if their “month” are the same.

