7.8 CENSORING RULES FOR TIME TO EVENT ANALYSES

The rules for censoring of time to event variables are described in the following. Incomplete dates for the new AML therapies which are used as censoring variable in some of the analyses will be imputed using the rules described in chapter 6.1.1 of the SAP. The imputations are done prior to the use of the new AML therapies as censoring variables, so that only complete dates are used for the censoring rules.

Rules for the use of new AML therapies as censoring variable in time to event analyses:

- Treatment with HDAC is regarded as new AML therapy
- G-CSF is not regarded as new AML therapy and therefore the treatment with G-CSF is not regarded as censoring variable.
- Treatment with decitabine, Azacitidine or hydroxyurea given only for up to 3 days are not regarded as new AML therapy and therefore not regarded as censoring variables
- Treatment with Methotrexate for the treatment of Crohn's disease is not regarded as new AML therapy and therefore not regarded as censoring variable.
- A new AML therapy that started and ended before Day15 of Cycle1 of the treatment phase of the study are not regarded as censoring variable in the time to event analyses.

-
- If a new AML therapy started before Day15 of Cycle1 of the treatment phase of the study and ended at or after Day15 of Cycle1 then the censoring starts at Day15 of Cycle1.
 - If a new AML therapy started at or after Day15 of Cycle1 of the treatment phase of the study then the new AML start date is taken as censoring timepoint.
 - If more than one new AML therapies are documented for one patient then only the start of the first therapy is used as censoring timepoint.

According to protocol only hydroxycarbamide (hydroxyurea) is allowed during the first 14 days of cycle 1; the rule for this treatment was enlarged to 28 days, using a pragmatic approach.

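### SAP 6.1.1 dates some incompletely recorded placebo new-AML therapies to 1 January, so they are ignored where the same pracinostat record is censored at Day 15

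*SAP*

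**What the plan says.** SAP 6.1.1 imputes incomplete new-AML-therapy dates by arm and calls the rules conservative.

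- **Placebo start.** Day missing: last day of the month. Year only: "31 December of the year documented or as 01 January if the year is the same as for treatment start". Nothing recorded: "the date of event is imputed as 01 January of the year when the study treatment started".
- **Pracinostat start.** Missing, or year-only in the treatment-start year: study treatment start.
- **Placebo end.** Day missing: first of the month. Year only: "as 01 January of the year. If the year documented is equal to the year of the start of the study treatment", then "the date of the end of the new AML treatment is imputed as the start date of the new AML treatment".
- **Pracinostat end.** Last day of the recorded month, or 31 December of the recorded year.
- **End missing or ongoing, both arms.** Last date known alive.

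Two general rules apply. One is an upper limit: "any imputed date should be before the date of death or the last day the patient was alive". The other orders the dates: "the end date of the therapy should be greater or equal to the start date of the therapy". Neither sets a lower limit at first dose.

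SAP 7.8 applies its censoring rules after imputation. "A new AML therapy that started and ended before Day15 of Cycle1 of the treatment phase of the study are not regarded" as censoring events. If the therapy began before that day "and ended at or after Day15 of Cycle1 then the censoring starts at Day15 of Cycle1". A therapy starting on or after Day 15 censors at its start.

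**The concern.** The placebo start rules choose a late date in every case but two. When the start is missing, or known only as the treatment-start year, the rule jumps to the earliest day of that year, usually before any study drug was taken. SAP 6.1.1 introduces these rules for therapies begun after, or together with, the end of study treatment, and a date before first dose does not fit that description.

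The consequence appears in SAP 7.8. When the end is also year-only in that year, the placebo therapy shrinks to a single day before Day 15 and drops out, while the same record in the pracinostat arm censors the patient at Day 15. The treatment code alone then decides whether follow-up after a new therapy counts.

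**Working it through.** The plan states no figure that depends on these rules, so there is nothing to reproduce. The check applies the rules of SAP 6.1.1 and then 7.8 to the same entries in each arm, with Day 15 = first dose + 14 days and survival past Day 15.

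**Example.** First dose 10 May 2018, so Day 15 = 24 May 2018; last known alive 15 March 2020 (illustrative dates). The start is either missing or recorded as 2018; both give the same result.

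| Recorded end | Placebo dates | Placebo result | Pracinostat dates | Pracinostat result |
|---|---|---|---|---|
| 2018 | 1 Jan 2018 to 1 Jan 2018 | ignored | 10 May to 31 Dec 2018 | censored 24 May |
| missing or ongoing | 1 Jan 2018 to 15 Mar 2020 | censored 24 May | 10 May 2018 to 15 Mar 2020 | censored 24 May |
| Nov 2018 | 1 Jan to 1 Nov 2018 | censored 24 May | 10 May to 30 Nov 2018 | censored 24 May |
| 15 Dec 2018 | 1 Jan to 15 Dec 2018 | censored 24 May | 10 May to 15 Dec 2018 | censored 24 May |
| 2019 | 1 Jan 2018 to 1 Jan 2019 | censored 24 May | 10 May 2018 to 31 Dec 2019 | censored 24 May |

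Two starts by five ends make 10 patterns: 2 differ by arm and 8 agree. The placebo start lies 129 days before first dose (1 January to 10 May).

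**End known only as the Day-15 month.** An end of May 2018 becomes 1 May for placebo (before 24 May, ignored) and 31 May for pracinostat (censored 24 May). This is the same split, and it disappears only if Day 15 is itself the first of the month.

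**All first-dose dates in 2018, start and end both 2018.** Placebo is ignored on all 365. Pracinostat ends on 31 December and is ignored only if Day 15 falls on or after 1 January, that is, first dose on or after 18 December (18 December + 14 days = 1 January). That is 31 − 18 + 1 = 14 dates, so the arms differ on 365 − 14 = 351.

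**Why a later end must be clearly later.** With end 2019, the placebo end is 1 January 2019. For first doses on 19–31 December (31 − 19 + 1 = 13 dates), Day 15 is 2 January or later, so placebo is ignored and pracinostat is censored.

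**Moving the placebo start alone.** Starting placebo at first dose but keeping end = start gives 10 May to 10 May. That is still before 24 May, so the therapy is still ignored.

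**Corrected rules (see the fix).** With placebo start = 10 May 2018 and year-only end = 31 December 2018, all 10 patterns give 24 May in both arms: 0 differ instead of 2. The May 2018 end also agrees. With start and end both 2018, the arms agree on all 365 first-dose dates.

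**Which analyses.** SAP 8.1 does not censor primary OS at later therapy. Censoring at new therapy is used in sensitivity analyses of OS (8.1.2), RFS and PFS (8.3), and in duration of CR and cCR and time to CR (8.3).

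**The case against.** **Arm-specific dating is disclosed and intended.** Early for pracinostat and late for placebo is the stated scheme, and ignoring a placebo therapy is its extreme. It stands that treating the arms differently is not in itself the error. But the same 1 January start leads to Day-15 censoring of placebo, the earliest censoring date SAP 7.8 allows, in 8 of the 10 patterns. A rule that gives the earliest or no censoring according to how the end was recorded is not a conservative choice.

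**A start before first dose can be genuine.** SAP 8.2 counts therapies begun earlier and continued into treatment, and Protocol 3.4.2 permits earlier hydroxyurea and one hypomethylating course. This stands, and it rules out a blanket first-dose floor: a start of 2018 with end March 2018 would then begin on 10 May, after it ended.

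**A natural remedy is to date all these placebo starts late.** A reader might infer this from the scheme. It would make all 10 patterns differ by arm, with placebo censored 190 to 661 days later than pracinostat, which enlarges the difference at issue.

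**A reader might also infer that placebo censoring is indeterminate in later years.** Start and end both 2019 give 31 December 2019 and 1 January 2019, 364 days apart in the wrong order. The documents do not support that inference: the ordering rule is written as a condition on the end, so the natural reading moves the end and leaves the censoring start in place. One clarifying sentence is enough.

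**Conclusion.** The point holds as a minor defect. For placebo starts that are missing or year-only in the treatment-start year, combined with an end that is year-only in that year or known only as the Day-15 month, the rules ignore a therapy that censors an identical pracinostat record at Day 15. In the year-only case the exception is a first dose on 18–31 December. This assumes survival past Day 15.

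The Day-15 mechanism reaches the new-therapy-censored OS and PFS sensitivity analyses and time to CR. A reader might infer from the list of censored endpoints that RFS and duration of CR or cCR are hit in the same way. They are not: those sets require response without interceding therapy, and the first scheduled response marrow is on Days 21–26 of Cycle 2 (Protocol 5.1.11), after Cycle 1 Day 15. There the rule could act only through who counts as such a responder, and the SAP does not say whether imputed dates decide that.

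The documents give no rate of partial dates. As an illustration only, assume that 20–40% of 500 patients start a new therapy, that 44–94 of those therapies start and end in the first-dose year (a simulated range resting on assumed treatment and therapy durations), and that 2–10% of these are year-only. That gives 44 × 0.02 = 0.9 to 94 × 0.10 = 9.4 records over both arms. The direction of any bias depends on the hazard after the new therapy, so none is claimed. SAP 6.1.1 asks that missing dates be avoided and lists the raw dates, and SAP 8.1.2 assesses balance for censored OS; none of this changes the rule.

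**What to change.** Amend SAP 6.1.1 for these cells only.

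1. Placebo start missing, or year-only in the treatment-start year: use study treatment start, as for pracinostat.
2. Placebo end year-only in the treatment-start year: use 31 December. Placebo end known only as the Day-15 month: use the last day of that month. Cap both at death or last known alive. Extending the year rule to the year in which Day 15 falls also closes the 19–31 December cell.
3. Do not apply the first-dose floor when the recorded end is before first dose. Treat that therapy as prior therapy and ignore it in both arms.
4. State that when imputation puts the end before the start, the end moves to the start.
5. State in 7.8 that the exemption for treatments of up to 3 days uses recorded dates only; otherwise an imputed one-day therapy could qualify.

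Make the edit from the rule text alone, without looking at which patients it moves, because SAP section 11 places version 5 after unblinding of the interim results. The cost is a few reworded lines and a small programming change. The downside is that these placebo starts are dated early rather than late, but their censoring already falls at Day 15 in 8 of the 10 patterns.
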